Interventions: The experimental intervention (spatial cognitive training) will comprise repeated practice of the spatial imagery task with feedback after each trial. Training will be conducted in the participant's home using an iPad issued to the subject at the initial visit, and live video communication with a research assistant at the CVNR over the internet. The iPad will be programmed to allow administration of the spatial imagery task. As in the version of the spatial imagery task administered at initial and final testing, audio cues will trigger mental navigation through the grid using audio cues, with haptic reinforcement via tactile overlays for the screen (to permit sensory facilitation of learning). Following each sequence traced, subjects will be asked whether the shortest path back to the origin intersects with the sequence traced or not. If the answer is incorrect, the research assistant will show the correct path for the subject to trace mentally and haptically. In the control intervention, subjects will be taught letter correspondences to the numbers (e.g. 1->A, 2->B and so on until 25->Y), using a similar setup and procedure as in the experimental intervention.

Behavioral measures: The following behavioral measures will be collected before and again after training with the experimental and control interventions: (1) Performance (directional accuracy and response time [RT]) on the spatial imagery task will be acquired during fMRI scanning. (2) In addition, pointing accuracy will be measured on the real-world path integration task in the MSL, in terms of the angular difference between the target of pointing and the actual initial position. (3) We will also measure performance, with standardized neuropsychological tests, at baseline as well as at post-training, on (a) spatial memory using a haptic version (produced in the [name] lab using textured blocks) of the Corsi block test (Kessels et al., 2000), (b) the verbal memory tests of immediate and delayed memory from the RBANS (Randolph, 1998) and (c) verbal working memory tested by the Forward and Backwards Verbal Digit Span test from the Wechsler Adult Intelligence Scale (Wechsler, 2008). A research assistant will be trained by the PI and [name], Co-investigator on this project, to administer all the tests, as well as the training procedures.

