Imaging measures: The following imaging analyses will be conducted on data acquired before and again after training with the experimental and control interventions: (1) A univariate contrast between the experimental and control conditions will provide insight into the brain regions responsible, and the **magnitudes of activation** in key brain regions will be assessed. (2) Multivariate pattern analyses (Kriegeskorte, 2008) will be used to assess **representational similarity in the neural representations of paths**. (3) Further, we will use **multivariate effective connectivity analyses**, which our group has considerable experience with (Hampstead et al., 2011; [name] et al., 2013; Lacey et al., 2014), to examine patterns of connectivity during task performance. (4) In addition, we will assess **resting-state connectivity** patterns using the activated regions as seeds. (5) Finally, we will also acquire diffusion tensor imaging (DTI) scans to assess **structural connectivity**.

Imaging design: The same spatial imagery task as outlined above will be used during fMRI scanning in an event-related design, with pseudorandomly interleaved trials of a control task requiring judgment of whether the majority of numbers in the audio sequence are odd or not. On each trial, the stimulus presentation will occupy 4s or 5s, depending on whether the sequence comprises 4 or 5 steps in the grid. These two trial durations will be interleaved in pseudorandom order, as will experimental and control trials. Participants will be verbally instructed to make their keypress response following the last auditory cue. A blank interval varying from 4-8s will intervene between trials: this jitter allows for better estimation of the signal on each trial than designs with a fixed inter-trial interval. Each run of trials will also include six pseudorandomly interspersed 10s blank periods for estimation of baseline signal. Functional runs will last 9min 20s, comprising a total of 40 trials (20 experimental and 20 control). 4 such runs will be conducted.

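### Can the fMRI control task (is the majority of the numbers odd?) be answered from sequence length and first number alone, and does that require a new control condition?

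*Combined protocol and SAP*

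**What the plan says.** Under Spatial imagery task, the protocol numbers a 5x5 grid from 1 to 25, row by row from left to right. Sequences have four or five steps and diagonal cues are barred. The text does not say how many cells one cue may move. Fig. 3, which may show it, is not available in the copy reviewed.

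Under Imaging design, imagery trials are mixed with control trials requiring a "judgment of whether the majority of numbers in the audio sequence are odd or not". On timing the section says: "On each trial, the stimulus presentation will occupy 4s or 5s, depending on whether the sequence comprises 4 or 5 steps in the grid". It continues: "These two trial durations will be interleaved in pseudorandom order, as will experimental and control trials". Runs are described as "comprising a total of 40 trials (20 experimental and 20 control). 4 such runs will be conducted". There is also a rest reference: "Each run of trials will also include six pseudorandomly interspersed 10s blank periods for estimation of baseline signal". No separate rule is given for building the control lists.

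Under Imaging measures, the control trials serve as the comparison: "A univariate contrast between the experimental and control conditions will provide insight into the brain regions responsible". Resting-state connectivity is then assessed in "patterns using the activated regions as seeds", without saying which contrast defines those regions. Under Behavioral measures, the only in-scanner performance listed is that "on the spatial imagery task will be acquired during fMRI scanning". Analyses bases inference on the group by session interaction for the behavioral measures, with similar two-factor ANOVAs for the imaging measures except DTI. It also names the regions of interest in advance.

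**The concern.** A control task for listening to and processing a number sequence should oblige the participant to process it. On the natural reading of the text (one-cell steps, same sequences in both conditions), the numbers alternate odd, even, odd, even. Sequences with an even count are then always tied, so the answer is 'not'. Sequences with an odd count take the parity of their first number. A participant who noticed this could stop tallying, and a correct answer would not show that the sequence had been tallied.

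At stake is how the imagery-minus-control contrast is interpreted. If control trials demand less attention or working memory than intended, some activation credited to spatial imagery could reflect that difference. The weakness would carry into the connectivity seeds if they are drawn from this contrast.

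**Working it through.** The plan states no figure on this point, so there is nothing to reproduce. The check is a parity argument, a full enumeration, and a comparison with the alternatives.

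**Inputs.** Row-wise numbering 1 to 25, four or five steps and no diagonals (Spatial imagery task); 20 control trials per run and 4 runs, so 20 x 4 = 80 control trials per session (Imaging design). Assumptions not in the documents: one cell per cue, and the same grid sequences on control trials.

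**Parity.** A horizontal neighbour differs by 1 and a vertical neighbour by 5. Both are odd, so each one-cell move flips parity.

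**Enumeration of one-cell paths without revisits.** Six numbers are included in case the start cell is announced in addition to five steps.

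| Numbers heard | Paths | Majority odd | Rule correct |
|---|---|---|---|
| 4 | 456 | 0 | 456 |
| 5 | 972 | 500 (all odd-first) | 972 |
| 6 | 2112 | 0 | 2112 |

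The rule is: even count, answer 'not'; odd count, answer by the parity of the first number. It is right on 456 + 972 + 2112 = 3540 of 3540 paths. Allowing revisits does not alter this: 912 of 912 four-number paths are ties, and at five numbers 1584 of 1584 odd-first and 0 of 1548 even-first paths have an odd majority.

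**Always answering 'not'.** With four- and five-number sequences equally frequent and paths drawn at random (both assumed), the share correct is 1 - 0.5 x 500/972 = 0.743, or 59.4 of 80. With odd-length shares of 40% and 60% it is 1 - 0.4 x 500/972 = 0.794 and 1 - 0.6 x 500/972 = 0.691.

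**If a cue may move one to four cells in a straight line (no revisits).** The rule fails. Four numbers give 2120 + 480 = 2600 odd majorities in 9200 sequences (28.3%) and 4560 ties (49.6%). At five numbers, first parity is right in (21936 + 18264)/58800 = 68.4%.

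Balancing the two answers within each length does not remove that cue:

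- four numbers: (2120/2600 + 3936/6600)/2 = (0.815 + 0.596)/2 = 70.6%
- five numbers: (21936/31896 + 18264/26904)/2 = (0.688 + 0.679)/2 = 68.3%

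**Cost of unrelated control numbers.** The grid has 20 horizontal neighbour pairs (difference 1) and 20 vertical ones (difference 5), a mean of (20 x 1 + 20 x 5)/40 = 3.0. For random distinct draws from 1 to 25 the mean difference is 26/3 = 8.7, and only 40 of 300 pairs (13%) are neighbours, against 100% on one-cell paths. Random draws also leave cues: 'not' is right 67% of the time at four numbers, and first parity 67% at five.

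**Cost of a different question on the same sequences.** Asking whether at least two numbers are multiples of 3 can be balanced: an 80-trial list gave 40 of 80 for length, for first-number parity and for the first number itself. The last number modulo 3 combined with length still scored 52 of 80 (65%) in the best of 3000 random lists. The difficulty of that question is unknown and would need a pilot.

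**The case for a change.** The strongest argument for acting is that both conditions are the natural reading. Imaging design describes each trial in terms of steps in the grid and gives no other source for control sequences. Real-world task sizes a floor cell to one average step and calls its sequences similar to the imagery ones. The answers are also unbalanced under other constructions: with multi-cell cues, 'not' is right on about 72% of four-number sequences (100% - 28.3%). A new list would be cheap before scanning, whereas a later change would break the comparison between sessions.

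The arithmetic stands, and so does the observation that step size and control-list construction are not written down. The step from there to a redesign is weak. A participant must first find the rule; nobody tells them, and no feedback on control trials is described. Even a participant using it must judge the first number's parity, hold it, and follow the sequence to its end to learn its length. That is still an attended, non-spatial number judgement. If the conditions do share the same sequences, only the instruction differs between them, which is a real strength of the design.

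**Conclusion.** No change to the plan follows. The shortcut is exact if each cue moves one cell and control trials reuse the grid sequences; the documents confirm neither, and it fails if cues can span several cells. The consequence is limited to a possibly weaker reference for the imagery-versus-control contrast, and for the seeds if they come from it. Whether participants would notice the rule cannot be judged from the documents. Control accuracy is not a listed measure, the rest periods give a second reference, and the regions are named in advance. No bias in a listed outcome, in Aim I or in the group by session interaction is shown.

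Step size and the source of control sequences are details that the investigators must settle in order to program the task, and answer balance can be looked at then. Altering the control condition would be a trade-off without a clear gain: unrelated numbers bring a certain stimulus mismatch, and a new question brings unknown difficulty and a residual cue of 52 of 80. Keeping the parity question on matched sequences is a fair choice.

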In previous work from our laboratory, we showed that acquired blindness is associated with impairment on a spatial imagery task (Occelli et al., 2014). Performance on this task correlated positively with scores on a validated index of real-world spatial navigational abilities, the Santa Barbara Sense of Direction Scale (SBSoDS) (Hegarty et al., 2002). Thus, spatial cognitive abilities represent a potentially important target for rehabilitation of individuals with vision loss, and the spatial imagery task offers a useful tool to both index and provide a training ground for spatial ability that can generalize to the real world. Studies in the normally sighted indicate that spatial training can indeed improve spatial skills but that individual differences are important to consider during training (Hegarty et al., 2008; Keehner et al., 2006; Fields and Shelton, 2006). Furthermore, the effects of such training can generalize to untrained spatial, but not verbal tasks (Wright et al., 2008), and spatial abilities are correlated across various tasks (Hegarty and Waller, 2004; Picard and Pry, 2009). However, there are no parallel published reports, to our knowledge, on the efficacy of such spatial cognitive training for low vision or blindness rehabilitation. Spatial cognition was highlighted as one of the areas of key strategic importance for research into low vision and blindness rehabilitation (National Eye Institute, 2012) – the panel responsible was co-chaired by the consultant of the present proposal, [name].

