In order to lay the groundwork for a future Merit Review proposal investigating the utility of spatial cognitive training in visual rehabilitation, the currently proposed SPiRE project seeks to establish the feasibility of such training in visually impaired participants over a telehealth interface, to obtain data on the effect size of the training relative to a control intervention to provide a basis for sample size estimation in a larger clinical trial, and to examine the relevant neural mechanisms so as to suggest possible synergistic interventions that would enhance the effects of spatial cognitive training. Importantly, the proposed work will examine the real-world generalizability of the training effects using physical walking spaces to assure relevance to rehabilitation.

Research Design and Methods

PARTICIPANTS

We will recruit 60 blind participants, randomized by our CVNR statistician into two groups. One group will undergo the experimental intervention (spatial cognitive training) and the other will undergo a control intervention involving letter-number matching. The participants will include women and minorities in proportion to the demographics of the veteran population attending the Atlanta VA. Working with our statistician, we calculated that this sample size has a power of 0.81 to detect an effect size of 0.9 with $\alpha=0.05$ and $\beta=0.19$. The randomization process should result in a balance between the intervention and control groups with respect to a range of variables, including age, sex, age of onset of visual loss, duration of visual loss and of loss of light perception, and comorbid conditions; any residual differences will be accounted for as covariates in statistical analyses.

Since the participants are blind or have low vision, they will need transportation to the CVNR, which will be provided via a contractual arrangement in place with the CVNR. Subjects will be compensated for their time at a flat rate of \$150 for participation in all sessions of the study. If they drop out or are otherwise unable to complete the study, compensation will be prorated for the number of sessions they participate in.

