Specific Aim I will test the hypothesis that spatial cognitive training of blind veterans on a spatial imagery task leads to improvements in **(a)** performance on the trained spatial imagery task and **(b)** real-world navigational ability, relative to a control intervention. If the hypothesis is supported, this would be a simple method of spatial cognitive training with real-world benefits that could eventually be administered via telemedicine. **Specific Aim II** will use functional magnetic resonance imaging (fMRI) to assess the neural changes associated with spatial cognitive training. The hypothesis is that those in the spatial cognitive training group will show enhanced activation in brain regions mediating spatial processing, such as the hippocampus and parietal cortex, as well as more differentiated neural representations of imagined paths. The benefit of pinpointing the neural loci of change is the identification of potential targets for application of converging rehabilitation approaches, e.g. transcranial magnetic or electrical stimulation over parietal regions; enhancing hippocampal neurogenesis through aerobic exercise. If the present proposal is successful, subsequent research will be needed to determine how best to incorporate such training into programs that complement current O&M training.

ANALYSES

In **Specific Aim I**, each behavioral measure will be subjected to a repeated-measures ANOVA with a between-subjects factor of group (experimental, control) and a within-subjects factor of session (pre-training, post-training); the null hypothesis will be rejected in case the interaction is significant at $\alpha=0.05$. If the interaction is non-significant, the Bayes factor will be calculated to ascertain whether this (less likely) supports the null hypothesis or (more likely) reflects insufficient power (Dienes, 2014); in the latter case, the data can be used to estimate the sample size for a subsequent study. In **Specific Aim II**, the imaging measures acquired (except

for DTI) will be subjected to similar two-factor ANOVAs as in Aim I, and statistical interpretations will follow similar lines.

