We predict that spatial cognitive training, but not the control intervention, will lead to improvements in performance on the spatial imagery task, its analog in the MSL, and the various functional neuroimaging measures. There may be transfer of spatial learning to the spatial memory task, but we do not expect transfer to the verbal memory and working memory measures, indicating the spatial specificity of training. We hypothesize that spatial cognitive training, but not training on the control intervention, will lead to increases in activation in cortex along the IPS and in the FEFs as well as in the hippocampus, increased strength of connectivity between these regions in the task and resting states, and also to more differentiated representations between different paths (i.e. their representations will show higher dissimilarity). The behavioral and neuroimaging measures obtained at baseline, including DTI measures of structural connectivity between the activated brain regions, will be tested as regressors to establish whether they predict changes in the repeated measures. This will be useful to examine the impact of individual differences in pre-training spatial and verbal abilities on the effects of training, and in the design of further studies aimed at targeting interventions tuned to individual performance in specific domains.

TIMELINE

First 2 months: Set up tasks and initiate recruitment

Next 20 months: Test and train 2 subjects per month, one in each group

Last 2 months: Analyze data and prepare publications

FUTURE DIRECTIONS

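### Adjust each outcome for its own baseline, and rest any claim about who benefits from training on a group-by-predictor term, which the plan does not state

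*Combined protocol and SAP*

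**What the plan says.** **Group comparison.** Under Analyses, Specific Aim I, each behavioural measure goes into a "repeated-measures ANOVA with a between-subjects factor of group (experimental, control) and a within-subjects factor of session (pre-training, post-training", and the null hypothesis is rejected if the interaction is significant at 0.05. The imaging measures other than DTI are treated in a similar way. No baseline-adjusted model is stated. The Participants section allows covariates only for imbalances left after randomization. Its examples are demographic and clinical, and an outcome's own baseline is not among them.

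**Individual differences.** The Analyses section adds that baseline behavioural and imaging measures, DTI included, "will be tested as regressors to establish whether they predict changes in the repeated measures". The stated use is to "examine the impact of individual differences in pre-training spatial and verbal abilities on the effects of training", and to help design later studies that fit interventions to the individual. The model is not written out and no group-by-predictor term appears.

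**Own baselines fall within that wording.** Under Behavioral measures: "The following behavioral measures will be collected before and again after training with the experimental and control interventions". Background and Significance says that "the spatial imagery task offers a useful tool to both index and provide a training ground for spatial ability", and also that "spatial abilities are correlated across various tasks".

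**Purpose and size.** Preliminary Studies gives one aim as "to obtain data on the effect size of the training relative to a control intervention to provide a basis for sample size estimation". Participants: "We will recruit 60 blind participants, randomized by our CVNR statistician into two groups". The Timeline provides for 2 participants a month over 20 months, one in each group.

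**The concern.** There are two separate matters.

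1. *Precision.* A change score uses the baseline with a fixed coefficient of 1. Regression adjustment estimates that coefficient and is usually more precise. A study meant to supply an effect size for a larger trial should take the tighter estimate when the baseline is collected anyway.

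2. *Prediction of change is not moderation of the training effect.* A baseline can predict change in both arms for reasons unrelated to training: regression to the mean, practice, or general prognosis. Only a difference between arms in that relation says who benefits from training. If the simpler association is reported, low scorers (or in some settings high scorers) could be taken to benefit most, and later studies targeted accordingly.

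**Working it through.** **Inputs.** From the documents: two groups, two sessions, 60 participants, alpha 0.05. Assumed, because the documents do not give them: pre-post correlation rho (0.5 to 0.9), SD ratio s = SD_post/SD_pre (0.9 to 1.25), and an equal split of 30 per arm. The plan has no figure of its own on this point to reproduce. Its one power statement (0.81 for effect size 0.9) bears only on which n to use. A two-sided t-test gives 0.929 at 30 per arm. At 20 per arm the figure is 0.792, or 0.812 by normal approximation. The Timeline also gives 20 × 2 = 40, i.e. 20 per arm. The sample size and Timeline need reconciling, but that is a separate matter. The figures below use 30 per arm unless stated.

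**Step 1: precision.** Set SD_pre = 1.
- Var(change) = s² + 1 − 2·rho·s
- Var(adjusted) = s²(1 − rho²)
- Difference = (1 − rho·s)², which is never negative and is zero when rho·s = 1
- CI-width factor = √(variance ratio × 57/56) × t(57)/t(58)

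Example, rho = 0.7 and s = 1: 0.51/0.60 = 0.85, factor 0.930.

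| CI factor | rho 0.5 | 0.7 | 0.8 | 0.9 |
|---|---|---|---|---|
| s = 0.9 | 0.825 | 0.875 | 0.896 | 0.908 |
| s = 1 | 0.874 | 0.930 | 0.957 | 0.984 |
| s = 1.1 | 0.913 | 0.969 | 0.993 | 1.009 |
| s = 1.25 | 0.954 | 1.000 | 1.009 | 0.984 |

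Simulated type I error is 4.9% to 5.1% for the change-score test and 4.9% to 5.2% for the adjusted test. At 20 per arm the largest factor is √(37/36) × t(37)/t(38) = 1.015.

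**Step 2: own baseline as predictor of change, no moderation.** Cov(baseline, change) = rho·s − 1, so the correlation is (rho·s − 1)/√(s² + 1 − 2·rho·s). At rho = 0.7 and s = 1 this is −0.3/√0.6 = −0.39. It is negative if rho·s < 1 and positive if rho·s > 1. Share of simulated trials with p<0.05 (20,000 per cell, bivariate normal, constant training effect), shown as trained arm only / all 60 with a group main effect:

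| | rho 0.5 | 0.7 | 0.8 | 0.9 |
|---|---|---|---|---|
| s = 0.9 | 94/100% | 82/98% | 75/96% | 69/94% |
| s = 1 | 82/98% | 58/87% | 41/70% | 22/40% |
| s = 1.1 | 67/93% | 33/59% | 16/27% | 5/5% |
| s = 1.25 | 43/72% | 11/18% | 5/5% | 22/41% |

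A group main effect does not remove the association. A predictor correlated 0.5 with the outcome's baseline gives 5% to 35% in the trained arm. At 20 per arm (rho 0.5, s = 1) the own-baseline rates are still 63% and 92%.

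**Step 3: a predictor unrelated to baseline but prognostic of change.** Take a predictor uncorrelated with baseline and correlated 0.3 with the post score equally in both arms, with rho = 0.7 and s = 1. Its correlation with change is 0.3/√0.6 = 0.39, the same size as in step 2. It rejects in about 59% of trials (trained arm) and 87% (all 60), with no moderation. Only a predictor unrelated to change altogether stays near 5%, so DTI is not exempt.

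**Step 4: the group-by-predictor term.** In the step 2 grid it rejects in 4.8% to 5.3% of trials, and in 4.8% to 5.4% when the trained arm's residual SD is 1.5 times the control arm's. For the step 3 predictor it is about 5%. It has two limits.
- *Ceiling.* With a constant latent effect of 0.9 SD and a cap 1.5 SD above the baseline mean (both assumed), it rejects in about 12% of trials at rho 0.7 and 19% at rho 0.8.
- *Power.* For own baseline at s = 1, 80% power needs slope differences of 0.670, 0.552, 0.464 and 0.337 at rho 0.5, 0.7, 0.8 and 0.9. Divided by common slopes of 0.5, 0.7, 0.8 and 0.9, these are 1.34, 0.79, 0.58 and 0.37 times the common slope. At 20 per arm power is lower.

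**Step 5: number of tests.** About eight behavioural measures, each as predictor and as outcome, give 8 × 8 = 64 terms. At 5% each, 64 × 0.05 ≈ 3 would be significant by chance.

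**The case against.** *The planned test is valid, so adjustment is a preference.* This is largely right. One might infer that the repeated-measures ANOVA is biased or wrong, and the documents do not support that: in a randomized comparison it holds its level. Nor does adjustment always help. For s of 1.1 or more and rho of 0.7 or more the CI factor is 0.97 to 1.01. If slopes differ strongly between arms the gain can vanish (simulated power 0.855 planned against 0.846 adjusted, at rho 0.7 and slope difference 0.5).

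*The plan may already contain the adjusted estimate.* Regressing change on group and own baseline gives the same group test as adjusting the post score. But the plan uses those regressors to predict change and does not take the group comparison from that model. The Participants provision applies only to leftover imbalance. Neither secures routine adjustment.

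*The regressor problem is conditional.* This stands as a limit on wording. A reader might infer that the plan rules out an interaction term. It does not; the term is only unstated. Many intended predictors are other measures, for which the own-baseline artefact is weaker, though step 3 shows that they are not safe.

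*The remedy is itself fallible.* This also stands. Ceilings, multiplicity and low power all apply to the interaction term, and the fix has to say so.

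**Conclusion.** The concern holds as an improvement to the analysis plan; the main Aim I test is sound.

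On precision, baseline adjustment changes CI width by a factor of 0.82 to 1.01 over the assumed range. The gain may be nil, and the cost is one degree of freedom.

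The second part is the stronger reason to act. Without a group-by-predictor term, the planned regressions cannot answer the question the plan sets for them. With no moderation, the own-baseline association is significant in anything from 5% of trials (where rho·s is close to 1) to nearly all of them. A predictor that is merely prognostic in both arms behaves in the same way.

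These sizes rest on assumed rho and s, normal scores and 30 per arm. The regressor analysis is exploratory and no Aim I decision depends on it, so what is at stake is the guidance carried into later studies.

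**What to change.** 1. For each behavioural measure and each scalar imaging measure, model the post-training value on group with that measure's own baseline as covariate. Report the adjusted difference with its 95% CI, and the observed rho and s, which a later sample-size calculation needs.
2. For every baseline predictor used (own baseline, other behavioural measures, imaging, DTI), fit group, predictor and group-by-predictor. Base any claim about who benefits from training on the group-by-predictor term only.
3. Report these tests as exploratory and low-powered, state how many terms were tested, and do not read a null result as absence of moderation.
4. Check bounded scores such as directional accuracy for ceiling effects before interpreting an interaction.

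The cost is analysis-plan wording and one degree of freedom per added term. For the group comparison, the CI is at most about 1% wider at 30 per arm and 1.5% at 20. No new data or participants are needed.
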